12.4. Prohibited, Previous and Concomitant Therapies

Any previous rosacea therapies must be stopped for the appropriate washout period as specified below and as noted in the exclusion criteria:

- Topical astringents or abrasives or preparations that contain spices or lime, medicated topical preparations applied to the face (prescription and OTC products) within 7 days prior to Baseline.
- Use of medicated cleansers on the face (e.g., benzoyl peroxide, salicylic acid, sulfur or triclosan) within 7 days of Baseline.
- Topical anti-rosacea treatments – 2 weeks prior to Baseline.
- Topical antibiotics, antimicrobials – 2 weeks prior to Baseline.
- Topical anti-inflammatories on the face such as corticosteroids, vasoconstrictors and non-steroidal anti-inflammatory drugs (NSAID) – 2 weeks prior to Baseline.
- Topical retinoids – 30 days prior to Baseline.
- Systemic rosacea treatments, corticosteroids, antibiotics – 4 weeks prior to Baseline.
- Systemic retinoids – 6 months prior to Baseline.

Other than the study products, no other topical medications are permitted to be used on the face. All topical or systemic medications listed above and under exclusion criteria are prohibited. Other prohibited treatments include but are not limited to astringents, toners, clarifying lotions, medicated shaving products, cosmetic procedures and chemical peeling products used on the face. A stable regimen of inhaled corticosteroids for stable medical conditions (in the 2 months preceding enrollment) and antibiotic treatment of an infection of less than 14 days are allowed during the study.

No medicated cleansers or moisturizers are allowed on the face. Only the sponsor-provided cleanser and moisturizer/sunscreen (or a study-approved cleanser or moisturizer/sunscreen) will be allowed to be used on the face during the study. Study product shall be applied to clean skin and no cleanser should be applied to the face within two hours of study product application. Approved moisturizer/sunscreen may be applied after 30 minutes or more of study product application. Patients who use make-up must have used the same brands/types of make-up for a minimum period of 1 month (30 days) prior to study entry and must agree to not change make-up brand/type or frequency of use throughout the study. Patients should not apply the moisturizer or sunscreen or combination of them or wear make-up during study visits as it may interfere with the evaluator's assessments.

All concomitant therapies used during the study must be recorded on the Concomitant Therapy electronic case report form (eCRF).

Therapies (medication and non-medication therapies) not restricted by the protocol may be used during the study for the treatment or prevention of disease or to maintain good health. Vitamins and mineral supplements are permitted at dosages considered by the investigator as reasonable for maintaining good health. Non-prohibited chronic therapies being used at Baseline (Visit 2) may be continued. Patients may use systemic anti-inflammatory agents [i.e., NSAIDs (ibuprofen or aspirin) for pain relief] as needed (with no more than 7 days of consecutive use) throughout the study. Prophylactic use of low dose aspirin (81 mg) is allowed. Patients may use acetaminophen for pain relief, as needed throughout the study.

Any changes in concomitant therapies during the study must be recorded on the Concomitant Therapy form at each visit. The reason for any change in concomitant therapies should be reported as, or in conjunction with, an adverse event except as noted below:

- Prophylactic therapies, such as vaccines, must be recorded on the Concomitant Therapy form, but the reasons for these therapies should not be reported as adverse events.
- Changes in therapy for pre-existing conditions that are not related to a worsening of the condition must be reported on the Concomitant Therapy form, but the reasons for these changes should not be reported as adverse events. The condition must be reported in the Medical History.

If a patient receives prohibited treatment during the study, the patient may be allowed to continue in the study at the discretion of the investigator and Sponsor / Medical Monitor.

Patients should avoid UV exposure by sun bathing or tanning parlors.

12.5. Precautions

The following precautions are to be taken during this study:

1. Patients should avoid contact of the study product with the eyes, mouth, and lips or on any cuts or broken skin. In case of accidental exposure, the eyes should be rinsed with plenty of water.
2. The study product should not be applied to cuts, abrasions, eczematous or sunburned skin.
3. Patients should wash hands before and after applying study product.
4. Patients should allow the treated area to completely dry for at least 30 minutes after applying the study product to avoid spreading it on other areas of the face (e.g., eyes, ears, neck, etc.) and pillow cases.
5. The study product should be spread evenly in a thin layer on each area of the face (chin, left cheek, right cheek, nose, left forehead and right forehead); excessive rubbing must be avoided.
6. The study product should not be applied more than once daily and patients should not use more than the recommended amount.
7. Patients should not wash their face more than 2 or 3 times a day.
8. Facial makeup (non-medicated) may be applied according to the patient's normal daily routine (but not prior to 30 minutes after study product application).
9. Patients should not apply moisturizers, make-up, creams, lotions, powders or any topical product they do not routinely use on their face
10. Patients should not cover the treated area with a bandage (occlusive dressing) or other types of dressing after applying the study product.
11. Patients should limit sun exposure, including sunlamps (non-prescription UV light sources); avoid tanning beds/booths/parlors and sauna while using the study product.
12. Patient should use moisturizer with SPF supplied by the Sponsor or from study-approved list product and protective apparel (e.g. wide- brimmed hat) when outdoors. Patients should wait approximately 30 minutes after study product is applied on the face before applying a sunscreen. Weather extremes, such as wind or cold, may be irritating to patients receiving treatment.
13. UVA/UVB treatments are also prohibited.
14. Patients must not wear make-up to any study visits, so as not to interfere with the evaluations. If a patient comes to his/her visits with make-up on his/her face, the patient will be allowed to wash his/her face with a non-medicated cleanser and must wait at least 30 minutes before any study evaluation is made by the Principal Investigator (PI) or Sub-Investigator (Sub-I).
15. Patients should consult the investigator with any questions regarding concomitant medications.
16. Abrasive cleansers or washes, alcoholic toners, astringents are prohibited throughout the study.
17. "Waxing" as a depilatory method should be avoided on skin treated with study product.
18. Patients should be informed that local skin reactions [dryness, burning/stinging, pruritus (itching), scaling/peeling] may occur.
19. Patients should minimize or not significantly alter consumption of any foods and beverages that might provoke erythema, flushing, and blushing (including spicy food, alcoholic beverages, and thermally hot drinks, including hot coffee and tea) throughout the study.

13. STUDY PROCEDURES

13.1. Study Patient Identification

When the patient signs the informed consent, he/she will be assigned a three (3)-digit patient number. The complete patient ID will consist of the 3-digit site number followed by the 3-digit patient number: e.g., [REDACTED] (first patient screened at site [REDACTED]). This number will remain with the patient for the duration of the study and will not be reassigned to another patient should the patient screen fail.

13.2. Screen Failure and Discontinuation Criteria

A screen failure is a patient who is not randomized/enrolled in the study due to ineligibility, after signing an Informed Consent Form, and would not have received study product. The Informed Consent Form signed by the patient should be kept with the source document for patients who do not pass the screening procedures. The documentation should include identification of the eligibility criterion or criteria that were and were not met. The patient should not be re-screened for this study without Sol-Gel's approval.

Although encouraged to complete the study whenever possible, patients are free to discontinue their participation in this study at any time and for any reason without prejudice. A patient may be withdrawn from the study prior to study completion for any of the following reasons:

- Investigator opinion that it is not in the patient's best interest to continue.
- Patient Request /Withdraw Consent – Whenever the patient decides it is in his/her best interest to withdraw.
- Lack of Efficacy/ Worsening of Condition.
- Adverse Event – when the investigator thinks it's in the patient's best interest
- Lost to Follow-up – Documentation confirmed at minimum by two phone calls and certified letter. Every effort should be made to capture an explanation for the lost-to follow-up event.
- Protocol Violation – When requirements of the protocol are not respected, especially when patient safety is concerned.
- Pregnancy.
- Unblinding of study product.

Study staff should make efforts to encourage patients to complete the study on time. If a patient prematurely withdraws during the study, every effort should be made to complete at least the Week 12/End of Study assessments.

In the case of patients who discontinue due to an Adverse Event, the Investigator will conduct follow-up contacts with the patient until the Investigator, Sponsor and Medical Monitor agree the event is satisfactorily resolved and/or stabilized.

Patients discontinued early from the study shall not be replaced.

13.3. Patient Screening and Enrollment

The study personnel will review the IRB approved informed consent form with each patient and give the patient an opportunity to have all questions answered before proceeding. The consent form must be signed by each patient before the patient is enrolled into the study. A copy of the signed consent will be given to every patient (or legally authorized representative) and the original will be maintained with the patients' records.

Patients that require a wash-out of more than 30 days from their initial informed consent/assent signing must be re-consented before any further study procedures can begin.

13.4. Assignment of Randomization

The patient randomization schedule will be a permuted block design stratified by investigational site. Blocks will be composed of 3 treatment assignments in a ratio of 2:1 study product and vehicle, respectively. Complete blocks from the randomization schedule will be allocated to investigational sites as they randomize patients. Patients will be randomized through the IWRS and assigned a unique randomization ID indicating treatment group. The study product supplies will be packed in 4 pumps per kit and will be numbered in a scrambled randomized method. The kits will be dispensed by the IWRS according to the randomized treatment group.

The first supplied pump in each kit is marked A (e.g. number of pump within a kit is XXXXA), at Visit 4/ Week 4 the patient will return the pump and will be dispensed with the next pump which is marked B. At Visit 5/ Week 8, the patient will return the pump and will be dispensed with a pump marked C. Pump marked as D may be dispensed to patients who lost/damaged/ran-out of study product.

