In the case of an emergency that requires unblinding, the Investigator can request to unblind the patient without prior contact with the Medical Monitor although follow-up between the Investigator and Medical Monitor must occur so that all parties are aware of the unblinding. Although it is recommended that the Investigator contact the Medical Monitor prior to unblinding any patient, in instances where this is not feasible or advisable the PI may directly access the patient's treatment assignment. In all situations, the Interactive Web Response System (IWRS) will be used to obtain treatment assignment information with limited access to only the above-designated individuals, and any unblinding will be documented as a protocol deviation.

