18.3. Study Products Packaging and Labeling

The study product (Encapsulated Benzoyl Peroxide Cream, 5%), S5G4T-1, and placebo for the study product (Vehicle Cream), S5G4T-2, will be packaged and labeled in 55-g airless pump. At the first 12 weeks of treatment, a double-blind technique will be used. In order to maintain the blind, the study product and vehicle will be supplied in identically-appearing labeled pump cartons. Neither the patient nor the investigational staff (sponsor, investigator, and evaluators) will know which treatment a patient is receiving.

The study products will be shipped to sites in blocks of three (3) products to keep ratio 2:1 between study product and vehicle. The study products will be labeled with the following:

- Protocol Number

- Patient Number
- Kit Number
- Pump Number
- Patient Initials
- Dispense Date
- Dispenser Initials
- Contains: one (1) pump of S5G4T-1 (Encapsulated Benzoyl Peroxide) Cream, 5% or its Vehicle Cream, 55 g
- Directions for use: Apply as directed, for topical use only.
- Storage conditions “Store at Room Temperature 20 to 25°C (68 to 77°F). Excursions permitted between 15 to 30°C (59 to 86°F).”
- Keep container tightly closed.
- Do not freeze and do not refrigerate.
- Keep out of reach of children.
- Study product warning. “Caution: New Drug - Limited by Federal Law to Investigational Use”
- Sponsor Information

Each Study Product Kit Box will contain four (4) pumps and will carry a two-part label with a perforation. The tear-off section of the label will be attached to the study product dispensing log at the time the study product is dispensed. The other label part must remain attached to the box. Both label parts will have spaces to enter the patient’s initials, date dispensed, dispenser’s initials. The constant label part shows:

- Protocol Number
- Patient Number
- Patient Initials
- Kit Number
- Randomization Date
- Contains: four (4) pumps of Encapsulated Benzoyl Peroxide (E-BPO) Cream, 5% or its Vehicle Cream, 55 g.
- Directions for use: Apply as directed, for topical use only.
- Storage conditions “Store at Room Temperature 20 to 25°C (68 to 77°F). Excursions permitted between 15 to 30°C (59 to 86°F).”
- Keep container tightly closed.
- Do not freeze and do not refrigerate.
- Keep out of reach of children.
- Study product warning. “Caution: New Drug - Limited by Federal Law to Investigational Use”
- Sponsor Information

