Pump usage will be demonstrated by the site personnel on a sample pump at the clinic to help assure the patient understands the procedure. The patient will be provided a set of instructions ([Appendix 1](#)) that includes study reminders and restrictions as described in this protocol. Patients will be instructed to bring the study product to each visit and to not apply study product one hour prior to the study visit. Patients should be instructed to store the study product at room temperature, not in the refrigerator or freezer and informed that the test article may bleach colored fabric.

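### The protocol tells sites that blocks are fixed at 3 (2 active, 1 vehicle), so one patient known to be on vehicle makes the other two in the block certainly active

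*Protocol*

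**What the plan says.** Protocol 13.4 sets out the scheme in three statements. The first is "The patient randomization schedule will be a permuted block design stratified by investigational site". The second is "Blocks will be composed of 3 treatment assignments in a ratio of 2:1 study product and vehicle, respectively". The third is "Complete blocks from the randomization schedule will be allocated to investigational sites as they randomize patients". Section 12.1 repeats all three. Section 18.3 carries the number into the supply chain: "The study products will be shipped to sites in blocks of three (3) products to keep ratio 2:1 between study product and vehicle".

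The plan also has safeguards. Kits carry numbers that "will be numbered in a scrambled randomized method", and "The kits will be dispensed by the IWRS according to the randomized treatment group" (13.4). Section 18.3 requires active and vehicle cartons to look the same. SAP 6.1.2 repeats 2:1 randomisation through the IWRS without giving a block size and changes nothing. Neither document describes varying block sizes or withholding the size from sites.

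On unblinding, Protocol 12.1 lets the investigator act without first reaching the Medical Monitor: "in instances where this is not feasible or advisable the PI may directly access" the assignment of that patient. Section 13.2 lists unblinding among the reasons for which a patient may be withdrawn. Neither section deals with the other patients in the same block.

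**The concern.** Whole blocks go to a site as it randomises, so a site's patients 1 to 3, 4 to 6 and so on form triplets that anyone holding the protocol can mark off. Each triplet contains exactly one vehicle patient. Knowledge of one patient can therefore pass to two others who remain in the trial and continue to be graded.

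This matters because Section 14 rests efficacy on investigator evaluation. The two co-primary endpoints are a five-grade global assessment and a manual lesion count, and the plan does not require an efficacy assessor who is separate from the staff who see safety and tolerability information. Knowing a neighbour's treatment could colour grading. Knowing the next assignment could influence enrolment, since some eligibility criteria are left to the investigator's opinion (for example exclusion 22).

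**Working it through.** **Inputs.** Block of 3 with 2 active (A) and 1 vehicle (V), within site: Protocol 12.1 and 13.4. Planned arms of 234 and 117, at up to 28 sites: Protocol 12.1. Pooling minimum of 10 active and 5 vehicle per site: SAP 8.1.7. The guess-accuracy values in step 4 are assumptions, because the documents give none.

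**1. Planned numbers.** 234 + 117 = 351, and 351 / 3 = 117 complete blocks. These hold 117 × 2 = 234 active and 117 × 1 = 117 vehicle, which matches the plan. The average site has 351 / 28 = 12.5 patients, or about 4 blocks.

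**2. What a known assignment reveals.** Only three orders exist: VAA, AVA and AAV.
- Vehicle patient known: each of the other two is active with probability 2/2 = 1.00 (unconditionally 0.667).
- Two active patients known: the third is vehicle with probability 1.00.
- One active patient known: each of the others is vehicle with probability 1/2 (unconditionally 1/3).

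For comparison, in a block of 6 (4:2) a known vehicle patient leaves each other member active with probability 4/5 = 0.80.

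**3. Upper bound on predictability.** Suppose every earlier assignment in the block is known. An assignment is fully determined once only one treatment remains in the block.
- Expected number determined in a block of a active and v vehicle: a/(v+1) + v/(a+1).
- Block of 3: 2/2 + 1/3 = 4/3, and (4/3)/3 = 44.4%. Enumeration agrees: 2, 1 and 1 determined positions in the three orders, or 4 of 9.
- Block of 6: 4/3 + 2/5 = 1.733, and 1.733/6 = 28.9%.
- Equal mix of blocks of 3 and 6, sizes known: (1.333 + 1.733)/9 = 34.1%.

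Best-guess accuracy comes from always choosing the treatment with more assignments left and scoring a tie as one half.
- Block of 3: (2 + 2.5 + 2.5)/9 = 77.8%.
- Block of 6, by exact recursion: 4.467/6 = 74.4%.
- Equal mix, sizes known: (2.333 + 4.467)/9 = 75.6%.
- Always guessing active, with no knowledge: 66.7%.

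**4. What a guess reveals.** Suppose staff suspect vehicle with sensitivity se and specificity sp. The probability that the suspicion is right, which is also the probability that both others are active, is (se/3) / (se/3 + 2(1 − sp)/3). Call it p. Each other patient is then active with probability p + (1 − p)/2.

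| se / sp (assumed) | Both others active | Each other active |
|---|---|---|
| no information | 0.333 | 0.667 |
| 0.5 / 0.8 | 0.56 | 0.78 |
| 0.8 / 0.8 | 0.67 | 0.83 |
| 0.9 / 0.9 | 0.82 | 0.91 |

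**5. Cost of mixing block sizes.** Take a site that stops at exactly 15 patients.
- With blocks of 3 it always has 10 active and 5 vehicle.
- With an equal mix, it misses the minimum only if patient 15 falls halfway through a block of 6 and that half-block is uneven.
- The chance that a new block starts after patient 12 follows from u(n) = ½u(n−1) + ½u(n−2), counted in threes: 1, 0.5, 0.75, 0.625, 0.6875. The chance that this block has size 6 is ½, giving 0.6875 × 0.5 = 0.344.
- The first three of a 4:2 block contain no vehicle with probability 4/20 and two vehicles with probability 4/20, so the half-block is uneven with probability 0.40.
- 0.344 × 0.40 = 0.1375, or about 14% of such sites.

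**The case against.** The best defence is that blinding is meant to keep assignments unknown, so the 44% is a ceiling that should not be reached. That stands. On the same ceiling basis, mixing block sizes improves best-guess accuracy by only about 2 points (77.8% to 75.6%), and the documents give no rate of unblinding or of correct guessing from which to estimate a realistic effect.

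The routes to knowledge are also narrow. Emergency unblinding under 12.1 must serve the patient's interest and alter clinical management. It goes through the IWRS and is logged as a deviation. It gives certainty about both neighbours only when the patient turns out to be on vehicle (prior 1/3). An active result moves each neighbour only to even odds.

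A reader might go further and infer that side effects or bleaching effectively unblind the trial. The documents do not support that. Section 18.5 has patients told that "the test article may bleach colored fabric", but it makes no distinction by arm, and 12.1 has patients instructed not to talk about the product with study staff. Section 7 reports irritation and burning in both groups of the early single-agent study. SAP 4 describes all three Phase 2 formulations, vehicle included, as well tolerated. Burning is also a disease symptom scored in the PAPSS. Such cues arise only after use begins, so predicting a third patient would need both earlier ones identified first. The pace of enrolment is not given.

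A reader might also infer that shipment in threes exposes kits. It does not: scrambled numbers, IWRS dispensing and matching cartons mean that a set of three shows the ratio and identifies no kit.

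These safeguards hide what a kit contains. They do not hide the block structure, so the deduction from a known vehicle patient remains.

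**Conclusion.** The point holds as an avoidable weakness in allocation concealment and blinding, and it is a minor one. Certainty requires a known vehicle patient or two known active patients. A guess transfers only as much information as it contains. The 44.4% and 77.8% figures are upper bounds that assume all earlier assignments in the block are known, and they should not be read as the share of patients who will be unblinded. The reasoning assumes that sites fill blocks in enrolment order, which follows from whole blocks being allocated as a site randomises.

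The documents show no actual bias. The planned 234 and 117 are exactly consistent with the scheme, and power is unaffected. The case for change is that both co-primary endpoints depend on investigator judgement, that each unblinded vehicle patient exposes two others who stay in the trial, and that the disclosure serves no purpose for sites.

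**What to change.** 1. Remove the block size from Protocol 12.1, 13.4 and 18.3 and hold it in the restricted randomisation file. The site-facing text need say only that permuted blocks within site keep 2:1. So that deliveries do not give the size away, kit shipments should preferably not come in matching sets of three.
2. Before randomisation starts, generate the schedule with blocks of 3 and 6 mixed at random within site. Even if sizes became known, the upper bound falls from 44% to about 34%. If they stay hidden it is lower, because staff cannot tell where a block ends.

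The first change needs only wording and has no statistical cost. The second needs a new IWRS list and allows slightly more imbalance within site: about 14% of sites stopping at exactly 15 patients would miss the SAP 8.1.7 minimum of 10 active and 5 vehicle and need pooling. If that is unwanted, withholding the block size alone still helps. Either change has its full effect only if made before sites hold the protocol and randomisation begins.
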